#### 3.1 Event Windows:

	• But , all requirements for randomization eligibility must be completed before randomization in Medidata.
Treatment initiation (Time 0) for first randomized intervention (BIO, INJ)	
 
Randomized treatment should start 0 days to 4 weeks after randomization in Medidata.
 
Note:
 
If treatment is initiated on the same day as the Randomization Visit, all randomization requirements (questionnaires and procedures) should be completed before treatment initiation.
 
The Time 0 date used to determine subsequent events dates in the Medidata EDC will be determined as follows: 
 
Time 0 for BIO = Date of Train Session 1
 
Time 0 for INJ = Date of the first injection
 
Time 0 for EMM responders = Date the randomization eligibility CFR is completed in Medidata (that is, date when participant is deemed to be ineligible for a randomized intervention as considered a responder to EMM).
 
For any participant who does not respond to EMM but who is also not randomized for any other reason, the Time 0 used to determine the schedule for the follow-up assessments will also be the date on which the randomization eligibility CRF is completed in Medidata.
 
 
 

Biofeedback (BIO) therapy (5 x 1- hour visits, with an optional 6 th )	Each Biofeedback Train session should be spaced with a minimum interval of 2 days and a maximum interval of 10 days from the previous session, with no more than two sessions in a calendar week. Preferred is one training session per week.
Injection (INJ) – 6- week follow-up	1 week before – 2 weeks after the target date determined from Time 0
3-month follow-up	1 week before – 3 weeks after the target date determined from Time 0
6-month follow-up assessment	1 week before – 3 weeks after the target date determined from Time 0
12-month follow- up assessment	1 week before – 3 weeks after the target date determined from Time 0
18-month follow- up assessment	1 week before – 3 weeks after the target date determined from Time 0
24-month follow- up assessment	3 weeks before – 3 weeks after the target date determined from Time 0
Optional treatment - initiation	Optional additional treatment initiation should occur within 0 days to 4 weeks after the 3-month visit post randomization.


the randomized int

The timeline for the

	follow-up assessments will continue to be determined from treatment initiation ( Time 0 ) of ervention even when participants who fail that treatment select a second intervention. Use participants who initially respond to EMM but are then randomized after they are reatment failures at the 3-month follow-up assessment will reset when they begin the

determined to be treatment failures at the 3-month follow-up assessment will reset when they begin the randomized intervention. For these participants, the timeline for subsequent events will reset based on the **Time 0** of their randomized intervention. These participants will be active in the trial for an additional 3 months so that they are able to complete the 24 months of follow-up following the start of the randomized treatment.

### 4.0 Outcome Measures

4.1 Primary Outcomes: There are three primary outcomes: efficacy, safety, and cost.

*4.1.1 Efficacy:* The primary efficacy analysis will be based on the proportion of responders in each treatment arm. A responder will be defined as an individual whose symptom diaries demonstrate at least a 75% reduction in the average weekly frequency of FI from baseline (prior to the EMM to the last two weeks of the treatment period preceding the 3-month post intervention follow up. The rationale for choosing a 75% reduction in the frequency of staining, solid and liquid stool incontinence as the primary outcome measure is that, both in focus groups and surveys we conducted, half of patients with FI reported that they did not consider a 50% reduction in FI episodes to be a satisfactory measure of treatment success; rather, they believed an improvement of 70-80% was necessary for a treatment to be considered successful.

The frequency of FI will be recorded on a paper diary. Patients will be asked to record (1) the time of each accidental bowel leakage (ABL), (2) the amount of leakage that occurred, (3) the rectal sensation that occurred prior to the event (no awareness, normal warning, or strong urge), and (4) the consistency of the leaked stool. Patients will also be asked to record (5) the time of any BM that occurred in the toilet even if this starts as an ABL and is finished by passing stool in the toilet, (6) the consistency of the BM using the Bristol Stool Form Scale, and (7) medications or other treatments employed. The primary outcome is based only on the number of FI events; however, the amount of stool lost and the type of sensation experienced before the leakage are needed to guide the BIO intervention, and the number and consistency of BMs and use of fiber or medications is used to guide the EMM intervention. Rather than use different diaries for each of these purposes, we will ask all subjects to use this paper diary throughout the intervention period and for two-week periods preceding all follow up assessments.

Previous studies have identified a number of limitations to paper diaries: (1) Missing data if subjects forget to complete the diary or if it is illegible. (2) Inaccurate data that may result if subjects forget to record events when they occur and then try to remember what happened at the end of the day or several days later. In previous studies, we provided patients with a pocket-sized paper diary to take with them throughout the day and asked them to transfer their symptom ratings from the paper diary to a website at the end of the day. If they failed to submit a report to the website within 12 hours, they were sent an email reminder or were telephoned. They were also reminded the next time they attempted to enter data, if the data for the previous day was missing, and they were given an opportunity to report on the previous day; however, they were not permitted to go back further than the previous 24 hours. They were also provided with bonus payments for not missing any diary reports. With this combination of techniques, we were able to obtain an average of 73 consecutive days of symptom diaries without interruption from 185 IBS patients varying in age from 18 to 84. However, there is concern that since advancing age is a risk factor for FI, the patients who enroll in this study will be older and less comfortable than young or middle-aged subjects with transferring data to the internet. Therefore, to avoid biasing enrollment against these older subjects, we decided to use paper diaries for this study. To ameliorate potential problems with missing or untimely data reporting we will (1) thoroughly train subjects in recording their diary information at enrollment, and (2) telephone subjects during the first two weeks that they keep the diary to ensure that they are able to record events on this paper diary when they occur.

To protect against experimenter bias, patients will be classified as responders or non-responders based on diary data entered into the electronic data capture (EDC) system at the end of EMM and at 3-, 6-, 12-, and 24-month follow-up. Once the diary data are entered, a calculation performed within the EDC system will determine which patients are non-responders eligible for randomization, and the same process will determine which patients are non-responders at 3 months so they can be offered alternative treatment.

*4.1.2 Safety:* Adverse events will be collected by participant interview and medical records review, as appropriate, at all clinic and follow-up assessments. Adverse events occurring in the period from the time that the participant is consented through the end of the participant's study involvement at the 24-month follow-up assessment should be documented (See **Section 9.2**). Adverse events will be classified as Serious Adverse Events (SAEs) if conventional criteria are met

or simply as adverse events (AEs). AE

severity will be graded based on common terminology criteria for adverse events (CTCAE). Relationship to treatment will be assessed by the treating clinician and reviewed by the Medical Safety Monitor for the purpose of determining which events need to be reported to the IRB, DSMB and NIDDK in an expedited manner. At the end of the study, relationship to treatment will be evaluated by comparing the incidence of specific AEs between treatment groups. AEs will not be collected on the bowel diary, but patients will be encouraged to contact the study coordinator any time they notice a new symptom or side-effect.

*4.1.3 Cost of care:* A primary endpoint is cost for each treatment from the payer, patient, and societal perspectives. For the payer perspective, we will tabulate the numbers and types of treatment visits and multiply these by Medicare authorized reimbursement rates. Patient costs will be obtained from an *Out-of-Pocket Cost Questionnaire* developed to collect information on amounts patients pay for non-prescription medications and absorbent pads. Estimated costs from the societal perspective will be the sum of payer costs, patient costs, and patients' productivity losses associated with FI as evaluated by the *Work Productivity and Impairment questionnaire* (WPAI). The WPAI is a widely used measure of work absenteeism, impairment while at work, and interference with daily activities.

A secondary endpoint is an analysis of the cost-effectiveness of the two treatments. The metric used for comparing cost-effectiveness is the quality adjusted life years. This calculation requires a health-related quality of life index, i.e., a generic health related quality of life scale that may be used to compare the morbidity-related impact of different disease states. Harvie and colleagues compared three of these health-related quality of life indices in a group of 200 women with fecal incontinence, urinary incontinence, and/or pelvic organ prolapse. The utility indices compared were the Health Utilities Index Mark 3 (HUI-3), the Euro-Qol (EQ-5D), and the Short Form 12 (SF-6). The HUI-3 and the EQ-5D were comparable in terms of their correlation with FI severity scales and their ability to discriminate between women with FI and those without. However, the EQ-5D is the only one that has previously been used to estimate cost-effectiveness for treatment of FI, and it was shown to be able to discriminate between SNS and another surgical treatment for FI.

*4.1.3.1 EuroQol 5D (EQ-5D):* The EQ-5D consists of 5 domains – mobility, self-care, usual activities, pain/discomfort, and anxiety/depression – with three possible responses indicative of severity of impact for each of the 5 single question corresponding to these 5 domains. It shows good convergent validity with other standard measures of health utility such as the HUI-3, and is able to discriminate between different treatments for FI. The EQ-5D is the most widely used health utilities instrument for assessing cost-effectiveness. This generic QoL measure will complement the disease-specific Fecal Incontinence Quality of Life Scale.

*4.1.3.2 Work Productivity and Impairment (WPAI)*. The WPAI will be used to measure cost from a societal perspective. It is a widely used measure of work absenteeism, impairment while at work, and interference with daily activities. The WPAI can be given in two forms: one of which measures the impact of general health problems and a second which measures the impact of a specific health condition. The WPAI has been shown to have good convergent validity with other measures of work and activity impairment as well as test-retest reliability and discrimination between health states. It has not been used to measure the impact of FI on work productivity but has been used in studies of overactive bladder and urinary incontinence, and it is sensitive to the benefits of a drug on absenteeism and activity impairment in patients with irritable bowel syndrome.

4.1.3.3 The Out-of-Pocket Cost Questionnaire. This is a new guestionnaire designed to collect information on the amounts patients pay for non-prescription medications and absorbent pads purchased for the self-management of FI. In an anonymous internet survey of people with FI (half of whom had not discussed this problem with any physician), we asked how they coped with FI on their own; the first three responses in order of frequency were wearing pads, taking antidiarrheal medicines, and limiting food intake when they had to leave the house. This suggests that purchase of pads and medications for diarrhea or constipation may be significant sources of cost for patients.

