### 2. SCHEMA

Study sequence is shown above for all steps following informed consent in Visit 1.

- Subjects who meet the inclusion criteria are first asked to keep a symptom diary for two weeks to determine whether they have an adequate amount of staining, solid or liquid fecal incontinence to be enrolled. The number of FI episodes during baseline will become the reference for judging whether they demonstrate a 75% reduction in the frequency of FI. For patients who have a variable pattern of FI and the investigator believes that the initial two-week diary data collection did not adequately capture the extent of the FI, then the baseline bowel diary may be kept by the patient for an additional two weeks.
- 2. Subjects who have an adequate amount of FI during baseline and who fulfill other inclusion criteria are enrolled in a 4-week EMM protocol to determine whether this will reduce their FI episodes by 75% or more. If it does, they are not included in the randomized trial but are scheduled to return at 3 months for a follow-up assessment. If the subject does not achieve at least a 75% reduction in FI, they are randomized to one of two therapies: BIO or INJ. Whether or not participants are EMM responders, data regarding ongoing adherence to the EMM prescriptions will be collected from participants at the end of the 1-month EMM period and then also at the 3-; 6-; 12-; and 24-month follow-up assessments.
- 3. Each treatment intervention follows a printed protocol document. The number of treatment visits varies somewhat, from 2-3 visits for INJ, and 5-6 visits for BIO.

At 3 months, all subjects who received a randomized therapy are assessed to determine whether they meet the criteria for treatment success. If they fail to demonstrate a 75% decrease in FI compared to baseline, they are labelled as treatment failures and are offered the opportunity to try the other randomization treatment or SNS. Those subjects who were initial responders to EMM but who are determined at 3 months follow-up to no longer be responding to EMM will be eligible to be randomized to one of the two treatment therapies (BIO or INJ). For all participants, follow-up assessments occur at 6, 12, 18 and 24 months. The 3-, 6-, 12 and 24-month follow-up assessments may be completed in-person or remotely. The more limited follow-up data collection at 18-month should always be collected during a telephone call.

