### 3.0 Study design:

The overall study design, shown in Figure 1, is an unmasked, multisite, randomized, parallel group study comparing the effectiveness of two treatments for moderate to severe FI. This study design builds on the core recommendations of the NIDDK Workshop for design of an ideal comparative effectiveness RCT. It is a parallel group design which has the following features:

- 1. *Baseline:* Patients will keep a daily symptom diary for two weeks prior to the Baseline visit to (a) document that they meet the minimum frequency required for inclusion in the study and (b) provide a reference value for assessing treatment response at the end of EMM and at 3, 6, 12, and 24 months follow-up points. Adverse events and cost will be reassessed at each in-person visit and at 3-, 6-, 12-, 18- and 24-month follow up assessments.
- 2. Enhanced medical management: All patients meeting inclusion criteria will first be treated with EMM for 4 weeks to identify those who really need a more expensive and more invasive treatment. The key components of treatment are patient education about the basic physiological mechanisms for defecation, diet and medication to normalize stool consistency, and pelvic floor exercises taught by printed instructions. (Section 6.1) Additional goals of the EMM protocol are (a) to ensure that patients randomized to INJ meet the accepted criteria by failing to respond to EMM, and (b) to document the efficacy and the durability of systematically applied, optimized EMM. This design is similar to the one used in the Heymen RCT which provides the strongest evidence for the efficacy of BIO. We believe the exclusion of patients

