who respond to the nonspecific treatment components that are included in the EMM protocol may make it easier to detect differential effects of BIO and INJ. Patients who are responders to EMM will be followed up 3 months later; those who remain responders will be continued on EMM and be followed for the remaining 24 months of the study. However, those who are no longer responders to EMM after 3 months will be invited to be randomized to BIO or INJ just like patients who failed EMM at the end of the initial run-in treatment, and all outcome measures will be assessed at 3 months from initiation of the treatment arm to which they are randomized. They will be pooled with other patients randomly assigned to the same treatment for the primary analyses and will be assessed at 6 months. Those subjects will participate for 27 months.

- 3. *Randomly assigned treatment:* The window for treatment to be initiated is 0 days 4 weeks after randomization. Based on a randomization scheme implemented by the Data Coordinating Center, each patient will be randomly assigned to BIO or INJ and treated as follows:
  - BIO will consist of 5 required one-hour training sessions which should, ideally, be spaced at weekly intervals; however, the window between visits is 2 10 days to accommodate participants' schedules as long as no more than two visits occur in one calendar week. A 6th treatment session will be made available for patients if it is shown through anorectal manometry that they are having trouble understanding directions given during the first five sessions. These will occur in the 5-6 or so weeks following the initiation of treatment. Treatment approaches will include strength training in all patients, sensory training for patients with hyposensitivity, and/or urge-resistance training for patients with hypersensitivity to the sensations caused by rectal distention. Home exercises will be assigned to patients to practice these skills, and these will be guided by a brochure.

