All treatments will continue to be active after the training period. The bulking agents injected in the INJ treatment will remain in place. For BIO, patients will be encouraged to continue to practice pelvic floor PROTOCOL VERSION: 10.0 (Approved: JUN 11, 2022). Comparative Effectiveness of Biofeedback and Injectable Bulking Agents for Treatment of Fecal Incontinence: The Fecal Incontinence Treatment (FIT) Study

exercises and enhanced awareness of rectal sensations following the initial training period. Patients who withdrew from the study or who fail treatment at 3 months will be evaluated as treatment failures in follow-up analyses of efficacy. Data will be collected from participants who switch to an alternative treatment at 3 months, but these data will not be considered in this analysis. Safety data will be collected at every visit and follow-up assessment. Patients who are responders at 3 months will continue to monitor symptoms for an additional 21 months (2 years total) whereas patients who are non-responders at 3 months will be retained as treatment failures in the long-term analysis of the comparative effectiveness of these two randomized treatments. For longitudinal assessments of safety, cost, and secondary outcomes such as quality of life and FI severity scales, statistical models will include data from follow up time points through 24 months.

- 7. Adjust for Expectation of Benefit: In a trial comparing behavioral and medical therapy, patients cannot be masked. The validated Credibility/Expectancy Questionnaire was developed to assess the patient's expectation of benefit after initial exposure to treatment and was used in previous studies to determine whether there is equipoise between the active and control conditions in behavioral treatment trials. In this study, which is unmasked from the patient perspective, we anticipate that many patients will not regard the treatments as equally credible; therefore, we will rely on randomization to balance the groups for average level of expectancy. We will also use the Credibility/Expectancy Questionnaire to assess individual differences in expectancy and will enter this into the analysis as a covariate to see whether it explains group differences in efficacy.

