*6.3 INJ of dextranomer:* This protocol is a modified version of the protocol used by Graf to ensure consistency across sites and safety of patients. Patients are treated prophylactically with oral antibiotics to minimize injection site infections. One ml of NASHA dextranomer is injected through an anoscope into each quadrant of the submucosa (4 ml total) approximately 5 mm above the dentate line. After each INJ, the needle is left in place for 10 seconds to avoid backward leakage of contrast through the injection channel. Following the INJ patients are counselled to use stool softeners (docusate sodium) until the first bowel movement and to use paracetamol as needed for INJ site discomfort. Prophylactic antibiotics will be administered for 2 days starting on the day of injection. Six weeks after initial INJ, patients return for evaluation, and if the patient has achieved less than 75% reduction in FI, a second INJ is given.

6.4 Comparison of elements of BIO and INJ:

Table 9 shows the elements of the two treatments compared to each	h other.
	rouior.

	Enhanced Medical Management	Biofeedback	Injection
Preparation	None	None	Diet restrictions; enemas; and antibiotics per the procedure SOP
Number of visits	2 visit + 2 phone calls	5-6 visits	2 visits
Visit duration	60 min 1 st visit; 15 min phone calls (Day 3; Day 14); 30 min last visit	60 min	45 min
Visit frequency	1 st and last visits (start of treatment and after treatment program has ended)	Up to 2 visits per week, spaced 2-10 days apart for first 5-6 weeks or so	0 and 6 weeks
Procedure	Daily sphincter exercises, meds to normalize bowel habits	Learn how to improve strength and rectal sensation	Bulking agent injected into rectal wall to narrow opening
Expected Adverse Events	None	None	Pain at injection site, bleeding, infection

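### Scheduled adverse-event questioning follows treatment visits, so between first treatment and month 3 BIO is asked 4-5 times and INJ once, which may under-capture INJ pelvic pain in the primary safety outcome

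*Combined protocol and SAP*

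**What the plan says.** Three statements tie active questioning about adverse events (AEs) to visits. Section 4.1.2: "Adverse events will be collected by participant interview and medical records review, as appropriate, at all clinic and follow-up assessments". Section 3.0, item 1: "Adverse events and cost will be reassessed at each in-person visit and at 3-, 6-, 12-, 18- and 24-month follow up assessments". Section 3.0, item 6: "Safety data will be collected at every visit and follow-up assessment".

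The number of treatment visits differs by arm: "from 2-3 visits for INJ, and 5-6 visits for BIO" (Schema, item 3). For BIO, section 3.0 says of the sessions: "These will occur in the 5-6 or so weeks following the initiation of treatment". Table 9 (section 6.4) gives their frequency as "Up to 2 visits per week, spaced 2-10 days apart for first 5-6 weeks or so". For INJ, Table 9 gives visits at 0 and 6 weeks, and section 3.1 allows the 6-week visit from 1 week before to 2 weeks after its target. The only check-in calls in section 3.1 belong to the EMM run-in.

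Section 4.1.2 also states: "AEs will not be collected on the bowel diary". The same sentence encourages patients to contact the coordinator whenever they notice a new symptom or side-effect. Of the diary, section 4.1.1 says: "we will ask all subjects to use this paper diary throughout the intervention period".

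The primary safety outcome (sections 5.2.2 and 8.1) is the percentage of participants with pelvic pain of grade II or higher, treatment site infection, or an SAE requiring hospitalization, between randomization and the 3-month assessment. The arms are compared by Fisher's exact test at alpha 0.05.

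**The concern.** A participant counts once any qualifying event is found, so the percentage depends on how often and how soon each arm is asked. Table 9 expects pain at the injection site, bleeding and infection in INJ and no adverse events in BIO. The arm expected to have events is therefore the one with no scheduled question for 5 to 8 weeks after the procedure. Short-lived pain in that interval may be forgotten or graded from memory, whereas pain in BIO is asked about roughly weekly. Section 4.1.1 itself warns of inaccurate diary data when events are recalled several days later.

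Safety is one of three primary outcomes, and section 4.1.2 plans to judge relationship to treatment by comparing event incidence between groups. Both uses need comparable ascertainment. Section 8.1 contains no analysis that addresses the difference, and analysis cannot recover events that were never elicited.

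**Working it through.** **Step 1. The plan's own power figure.** Section 5.2.2 states 83% power for 0% against 10%, with 78 BIO and 92 INJ participants and alpha 0.05 (taken as two-sided; the plan does not say). Pooled normal approximation:

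- pooled rate = (78 × 0 + 92 × 0.10)/170 = 0.0541
- SE under the null = √[0.0541 × 0.9459 × (1/78 + 1/92)] = 0.0348
- SE under the alternative = √(0.10 × 0.90/92) = 0.0313
- power = Φ[(0.10 − 1.96 × 0.0348)/0.0313] = Φ(1.015) = 84.5%

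With 9/92 in place of 10% this gives 83.6%. The stated figure is thus reproduced to within 2 points. Exact enumeration of the two-sided Fisher test gives 90.8% at 10% and 89.6% at 9/92. That difference is conservative and is not part of this point.

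**Step 2. Scheduled questioning by arm, from Time 0 to month 3.** Time 0 is the first BIO session or the first injection (section 3.1).

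| | BIO | INJ |
|---|---|---|
| Treatment visits from Time 0 | 5-6 | 2 (weeks 0 and 6) |
| Plus the 3-month assessment | 6-7 | 3 |
| After first exposure, before month 3 | 4-5 | 1 |
| Longest gap in the treatment period | 10 days | 35-56 days |

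The INJ gap is 6 − 1 = 5 weeks to 6 + 2 = 8 weeks. The Schema's upper figure of 3 INJ visits does not close it if the extra visit is for preparation, since that would precede the injection.

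The imbalance belongs to about the first six weeks. BIO then has its own unasked stretch from the last session to month 3, while INJ is seen at week 5 to 8.

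**Step 3. Which components are exposed.**

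- Hospitalization and treated infection usually leave a record, so records review can find them late.
- Pelvic pain of grade II or higher need not leave one. It rests on recall at week 5 to 8 or at month 3, or on the patient making contact.

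**Step 4. How few events decide the test (illustration).** The plan expects 9/92 in INJ and 0/78 in BIO. With zero BIO events and k INJ events, the two-sided Fisher p-value is [C(92,k) + C(78,k)]/C(170,k), because for the k below only the two extreme tables are at least as unlikely as the one observed:

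- k = 6: 0.0233 + 0.0084 = 0.032, significant
- k = 5: 0.0441 + 0.0189 = 0.063, not significant

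So 9 − 3 = 6 recorded events still reject and 9 − 4 = 5 do not. If more frequent questioning turned up one BIO event, 7/92 would give p = 0.071 and 8/92 would give p = 0.040. The requirement would then rise from 6 to 8.

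These are thresholds. They do not estimate how many events would be missed.

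**The case against.** The case on the other side has weight.

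- **Other routes exist.** Both arms can contact the coordinator at any time, both have records review as appropriate, and both are asked at 3 months about a cumulative yes/no outcome. The long INJ gap is a gap in scheduled questioning, and an event can be captured before the gap ends. This stands and narrows the concern mainly to pain. It does not remove it: patient-initiated contact is passive, records miss untreated pain, and the 3-month question relies on recall.
- **Unseen manuals.** Section 6.0 refers to detailed procedure manuals, which are separate from the supplied text. A post-injection call specified there would weaken or answer the point. This stands as a condition.
- **The Table of Measures** marks AE assessment only at baseline, randomization and follow-up. It has no treatment-visit columns, however, and three statements in the text say AEs are asked about at every visit.
- **Different visit counts are inherent** in comparing these treatments. True, but asking the same safety questions at the same times does not require the same visits.

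Three stronger readings are tempting, and the documents do not support them.

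- A reader might infer a definite loss of power. With an assumed 80% capture of INJ events, Fisher power falls from 89.6% to 73.5%. But no capture rate is given, BIO is held at 0% in that calculation, and the 9.8% planning rate is close to the 9.6% reported in the published injection trial, which is already a captured rate.
- A reader might cite the 3-month ultrasound in INJ as further unequal detection. It is optional, serves to monitor migration of the bulking agent, and would if anything raise detection in INJ, the opposite direction.
- A reader might conclude that the two safety percentages cannot be compared at all. The shared 3-month assessment and the other common routes do not bear that out.

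**Conclusion.** The concern holds in limited form. Followed as written, the plan asks BIO about adverse events 4-5 times and INJ once between first exposure and month 3, with 5 to 8 weeks unasked after the first injection. The likely effect is under-capture of pelvic pain of grade II or higher in INJ relative to BIO, which would understate any INJ excess. The size is unknown and cannot be derived from the documents. What can be said is that few events decide the result: at the plan's expected counts, missing 4 of 9 would move the Fisher test from significant to not.

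This rests on three assumptions: that questioning does take place at every treatment visit, that no equivalent post-injection contact is specified in the procedure manual, and that some qualifying pain resolves before week 5 to 8 and is recalled imperfectly. The plan should be amended, but the point does not invalidate the primary safety analysis.

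**What to change.** 1. Check the INJ procedure manual. If it already provides contacts equivalent to the BIO sessions, with the same questions, cite them in section 4.1.2 and skip step 2.
2. Otherwise amend section 4.1.2. For participants not yet past 3 months, ask the same short scripted questions on the qualifying events (pelvic pain and its severity, treatment site infection, hospital stay) in both arms at the same times from Time 0 to month 3. Use a diary item, or the e-mail link and paper fallback already described in section 7.2.3. Section 4.1.1 promises the diary only for the intervention period and the two weeks before follow-ups, so a diary item would need its coverage stated. The paper option matters because section 4.1.1 doubts that older participants will report online.
3. Keep the primary safety definition, its data sources and Fisher's test.
4. For each qualifying event, record how and when it was first found.
5. Add to section 8.1 a sensitivity analysis of all participants restricted to events found at ascertainment points common to both arms, with those points listed in advance. It may drop a BIO event that was noted at a session and not re-entered at month 3, so read it beside the main analysis.

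**Cost:** an amendment, one form item, slightly more participant burden and data entry, and grading and clinical review of the extra reports. No extra visits are needed. There would be two ascertainment regimes across the enrolment period, and the report should say so. Events never elicited from participants already past 3 months cannot be recovered; for them only steps 4 and 5 help.
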